## 8.0 RECORDS TO BE KEPT

- Subject demographics & locator forms
- Subject consent forms
- ACASI questionnaires
- HIV testing forms
- Hepatitis C testing forms
- Audio recordings of interviews
- De-identified transcriptions of interviews
- Paper-based primary care provider surveys
- Handwritten notes from individual interviews
- Agency and service provider referral lists
- Participant intervention files (paper and virtual)
- DHS data on UG3 participants
  - COVID-19 infection, death, hospitalization, testing, and vaccination data
  - Fatal and nonfatal drug overdose data
  - Hepatitis vaccine records

## 9.0 PROTECTIONS AGAINST RISK

### A. Characteristics of human participants

**Individuals in the cross-sectional and client interview (UG3)** phases will be eligible for enrollment if they are 15 years of age or older, have injected any drug in the past 1 month, and reside in a rural community. Rural residence will be determined by ZIP code, which will be programmed in the screening instrument on REDCap. The eligibility form will classify a participant as a rural resident if the ZIP Code’s RUCA Approximation is greater than or equal to 4, or if they live in a catchment area of the SSP. **Providers** will be eligible if they are employed by an agency that serves opioid users. All study participants must be capable of communicating in English.

**Individuals in Phase 2 (UH3)** will be eligible if they are 18 years of age or older, have injected any drug in the past 1 month, and reside in a rural community.

## **B. Inclusion of Women and Minorities**

**Minorities:** The study will include people of all races and ethnicities proportional to rural population of injection drug users accessing services.

**Women:** Women will be included in the study proportional to rural population of injection drug users accessing services.

## **C. Participation of Minors**

**Phase 1 (UG3).** Minors ages 15-17 will be eligible to participate if they meet other eligibility criteria. Under the applicable federal regulations (45 CFR § 46.402(a)) “children” are persons who have not attained the legal age for consent to treatments or procedures involved in the research, under the applicable law of the jurisdiction in which the research will be conducted. Under Wisconsin statutes, minors age 15-17 may consent for STI testing and treatment, HIV testing, and alcohol or drug abuse assessment, evaluation, or treatment (outpatient). Thus, minors ages 15-17 are not “children” for purposes of the applicable regulations with respect to these tests. Additionally, the IRB will be asked to determine if this research protocol is designed for a subject population for which parental or guardian permission is not a reasonable requirement to protect participants and may waive the parent/guardian consent requirement. Federal regulation requires an “appropriate mechanism for protecting the children who will participate as subjects” as a substitute for parental consent. This will be accomplished by having an adult counselor from an advocacy organization available by telephone for minors to discuss the consent or other concerns. The consent document will notify minor participants that such resources are available if needed, and all research staff will be prepared to link clients to a local agency belonging to the Child Advocacy Centers of Wisconsin (<http://www.cacsofwi.org>).

**Phase 2 (UH3).** No minors will be participating in this phase of the study.

## **D. Protection of Incarcerated Individuals**

For Aim 3, our program is a 12-week intensive case-management program. Therefore we want to ensure that participants who become incarcerated have a way to re-engage with the study and intervention once they are released from jail or prison. If it is learned that a research participant is incarcerated at any time in the study, they will be immediately un-enrolled and research activities will be suspended. Participants in the intervention arm may receive contact from the prevention navigator to notify them of this and explain the process. No data will be collected from the participant during this time. Upon release, participants may contact Vivent Health staff to re-enroll in the study. The consent document will be reviewed with the participant at this time to re-assess willingness to participate. Participants can take their assessment after 2.5-5.5 months from baseline or follow up assessment. If the opportunity to take the assessment is no longer available, then we treat it as missing.

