**Survey and needs assessment.** The primary source of data collection in all three groups of the study will be from the ACASI questionnaire, administered at 0 months (baseline), 3 months, and 6 months from enrollment. All surveys will be administered on a tablet using the ACHESS application, by the participant accessing the survey in ACHESS on their smartphone or web browser on their own time, or over the phone. The data will be securely stored at UW-Madison and erased from the tablet if

applicable. The survey will consist of multiple choice questions designed to efficiently assess drug use history, access and utilization of prevention services, readiness for intervention, and injection related risk behaviors. The final survey a participant takes will include exit questions to help us evaluate and improve the program. Participants enrolled in the intervention between February 1, 2023 and March 31, 2023 will complete the baseline and 3 months ACASI questionnaire only.

**ACHESS.** All participants will complete study assessments using the ACHESS application. ACHESS can be accessed by downloading the application to a smartphone or via a web browser. Participants may also take part in optional non-research activities within the ACHESS app. These activities include: 1) posting on discussion boards, 2) utilizing the private message function to communicate with study staff or other participants, 3) viewing local community resources and their contact information, 4) viewing and saving motivational quotes of the day and logging thoughts of gratitude, and 5) accessing study staff contact information.

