**Laboratory-based confirmatory testing and specimen handling.** Specimens received by WSLH will be processed for confirmatory testing per standard protocols (see Facilities and Resources for details). After completing the required testing and reporting test results to the testing agency and the WI Surveillance System, WSLH staff will store plasma specimens in preparation for shipping to the CDC and/or GHOST laboratories, as described in Section 5.2

**Collection of baseline demographic and risk behavior data.** Similar to Aim 1, we developed strategies to ensure that research activities are minimally-disruptive to the daily, core prevention activities of Vivent Health staff. Our pilot studies within SSPs have shown that this is essential for ensuring study protocol fidelity, maintaining high-quality data collection, and maximizing client willingness to participate. We will take advantage of existing data collection forms that are used

during HIV and HCV testing encounters to capture necessary individual-level data elements. All publicly-funded HIV testing sites in WI are required to use a uniform data collection and reporting system called Evaluation Web (Luther Consulting, LLC, Carmel, IN). Rapid HCV testing supported by WI DHS requires that agencies report client-level data using the Wisconsin Electronic Disease Surveillance System (WEDSS). With participant consent, the paper data collection forms used to capture the required demographic and risk behavior information will be transmitted to the UW-Madison based study coordinator via secure fax-to-PDF system, and will be stored on an encrypted server in a directory separate from other study data.

**Medicaid and Health Care Utilization Analysis.** We will link multiple existing datasets at the individual-level to evaluate the effects of the intervention health care use. These include the WI Department of Corrections (DOC) administrative dataset, Medicaid enrollment and claims data, WI State Laboratory of Hygiene (WSLH) HCV test records, WI Department of Health Services HCV Surveillance data, and the new county-level data resource developed through the activities under Aim 2a.

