HIV DIAGNOSIS AND TREATMENT (HHIHIV SERIES)	Questions on whether participant has been tested for HIV, last HIV test date, test results, date of diagnosis, HIV treatment
HCV DIAGNOSIS AND TREATMENT (HHIHCV SERIES)	Questions on HCV diagnosis, treatment for HCV, and main place for medical care for HCV
BACTERIAL INFECTIONS	Hospitalization of serious bacterial infection, date of hospitalization
ACCESS TO MEDICAL CARE	Main place participant received medical care, barriers to care

KESSLER DISTRESS SCALE (KES SERIES)	Questions on participants anxiety and depressive symptoms in the last 30 days
PTSD SCALE	Questions on whether participant experienced adverse event, and symptoms experienced after adverse event
ACCESS TO PREVENTION AND TREATMENT (ACC SERIES)	Questions on accessibility to condoms, HIV treatment, HCV treatment, STI treatment, buprenorphine, naloxone, clean syringes, vaccinations, infection information
CRIMINAL JUSTICE	Times law enforcement has stopped and searched participant, number of arrests, probation in the last 6 months, days they were in jail
SEXUAL RISK (SXR SERIES)	Number of partners in the past 30 days, trade sex for drugs, last time they had vaginal or anal sex, sex without a condom, sex without a condom and injected drugs, sex with HIV+
DEMOGRAPHICS	Main source of income, services received, relationship status, student status, pregnancy status, forms of birth control, homelessness, transportation, health insurance
RDS	Questions on their network of people who inject drugs
RAPID RESULTS	Results from HIV, HCV, and Syphilis testing that was done that day
DUP_ID	Possible participants that entered the study more than once
Qualitative Participant Interviews	
All transcripts were stripped of the following information:	Names Geographic subdivisions smaller than a state All Dates Telephone numbers FAX numbers Email addresses Social security numbers Medical record numbers Health plan number Account number Certificate/license number License plate number Device identifiers/serial numbers Web urls Internet protocol addresses Biometric identifiers Full face photos and comparable images

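### The incarceration rule in section 9.0 D may lose Aim 3 follow-up unequally by arm, and its chained assessment window can forfeit an obtainable 6-month visit

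*Combined protocol and SAP*

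**What the plan says.** Section 9.0 D sets the Aim 3 rule in five steps.

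- **Trigger:** "If it is learned that a research participant is incarcerated at any time in the study, they will be immediately un-enrolled". Research activities are suspended and no data are collected meanwhile. The section describes no active check for incarceration.
- **Notice:** "Participants in the intervention arm may receive contact from the prevention navigator to notify them of this and explain the process". Nothing equivalent is written for controls.
- **Return:** "Upon release, participants may contact Vivent Health staff to re-enroll in the study". This route covers both arms and has no stated deadline; consent is reviewed again.
- **Window:** "Participants can take their assessment after 2.5-5.5 months from baseline or follow up assessment".
- **Missed assessments:** "If the opportunity to take the assessment is no longer available, then we treat it as missing".

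Section 5.4 schedules the survey differently: it is "administered at 0 months (baseline), 3 months, and 6 months from enrollment".

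Section 9.0 H describes routine contact. Vivent Health staff make all follow-up contacts with intervention participants, including reminders, check-ins after important appointments and booster sessions, with no stated cap. Controls are contacted by the project manager to remind them to schedule visits, at most 3 times between research visits.

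The Aim 3 analysis in section 6.0 names generalized linear mixed models. Neither it nor the sample-size text in section 7.0 gives a missing-data assumption, a sensitivity analysis or an allowance for loss.

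**The concern.** A rule triggered by what staff happen to learn works evenly only if they are equally likely to learn it in both arms. Someone in a 12-week case-management program who stops responding is more likely to be noticed than a control who receives a few scheduling calls. The same stay in custody could then suspend one participant and pass unrecorded in the other. Return may differ too, because the only written explanation of the process is for the intervention arm and re-entry goes through Vivent Health staff, who already make that arm's follow-up contacts.

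If recently incarcerated people report poorer access to services, losing them at different rates shifts the arms' observed proportions even when navigation has no effect. That would bear on the between-site comparison, (B) in Appendix 1 section 1.7. A mixed model does not remove such a shift when missingness depends on an incarceration that is not in the model.

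The window raises a separate issue, the same in both arms: it can close a 6-month visit that is not yet due.

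**Working it through.** **1. The plan's own figure.** Section 7.0 gives 270 intervention and 135 control participants, 28% versus 42%, and 80% power. I assume two-sided alpha 0.05, since the 5% is stated only for Aim 1.

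- Pooled proportion = (135×0.28 + 270×0.42)/405 = 0.3733.
- Null SE = √[0.3733×0.6267×(1/135 + 1/270)] = 0.0510.
- Alternative SE = √[0.28×0.72/135 + 0.42×0.58/270] = 0.0489.
- Power = Φ[(0.14 − 1.96×0.0510)/0.0489] = 0.794.

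The stated 80% reproduces, with no allowance for loss. With 20% lost in both arms (an assumed rate) power is 0.697.

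**2. Possible bias with no true effect.** The documents give no rate of incarceration, detection, return or retention, so every rate here is assumed. Let q be the share jailed and released before the visit, with a strongly-agree rate of 32% in those not jailed and 12% in those jailed. At q = 0.2 the overall rate is 0.8×32% + 0.2×12% = 28%, the planning value.

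The jailed share still assessed is j = q×[(1 − learned) + learned×return]. The observed proportion is [(1 − q)×0.32 + j×0.12]/[(1 − q) + j].

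| Learned, int. / control | Return, int. / control | q | Observed int. | Observed control | Difference (points) |
|---|---|---|---|---|---|
| 80% / 30% | 0 / 0 | 0.2 | 31.0% | 29.0% | +2.0 |
| 80% / 30% | 0 / 0 | 0.4 | 29.6% | 25.6% | +4.0 |
| 80% / 30% | 40% / 15% | 0.2 | 29.7% | 28.9% | +0.8 |
| 80% / 30% | 40% / 15% | 0.4 | 26.9% | 25.4% | +1.5 |
| 50% / 50% | 40% / 15% | 0.2 | 29.0% | 29.5% | −0.5 |

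In the first row j is 0.2×0.2 = 0.04 for intervention and 0.2×0.7 = 0.14 for control, giving 0.2608/0.84 and 0.2728/0.94. Loss with no returns is 16-32% (0.8×q) against 6-12% (0.3×q).

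With 80%/30% detection and 15% control return, the bias vanishes when 0.8×(1 − r) = 0.3×0.85, that is, when r, the intervention-arm return, is about 68%.

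A second set of assumptions reverses the sign. Hold the overall rate at 28% in both arms, assess no jailed controls, and assess half of the jailed intervention participants. The rate in those not jailed is then (0.28 − s×p)/(1 − s), where s is the share jailed and p their rate.

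- s = 10%, p = 14%: −0.8 points.
- s = 20%, p = 5%: 30.6% versus 33.8%, −3.2 points.
- s = 30%, p = 5%: 32.1% versus 37.9%, −5.8 points.
- p = 28%: zero.

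If all jailed intervention participants are assessed and still no jailed controls, the range is 0 to −9.9 points.

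**3. The window, traced by case.**

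- First follow-up done at month 3: the next window is 3 + 2.5 = 5.5 to 3 + 5.5 = 8.5 months, so the 6-month visit is covered.
- Extremes of the chain: 2.5 + 2.5 = 5 to 5.5 + 5.5 = 11 months from baseline.
- Released at month 5.4 with no prior follow-up: an assessment is still allowed, and a second falls at 7.9 to 10.9 months.
- Released at month 5.6 with no prior follow-up: the baseline window closed at 5.5 and there is no follow-up assessment to count from. Read literally, neither assessment can be taken, although month 6 has not arrived.

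**The case against.** Several stronger readings are tempting, and the documents do not support them.

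- **That participants cannot return after 5.5 months.** Re-enrollment has no stated deadline; 2.5-5.5 months is an assessment window that restarts at each completed follow-up.
- **That controls are never told how to return.** The text is silent about them, and even intervention-arm contact is only permitted. What everyone is told at consent cannot be seen in the review copy. The stated return route is the same in both arms.
- **That comparison (B) is biased, and in favor of navigation.** No rates exist. Closer contact raises detection, which removes people, and may also raise return, which brings them back. The net sign is undetermined.

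Other points on that side also carry weight. Controls use the syringe service, complete locator forms and have ACHESS messaging, and participants may be paid monthly to update contact details, so the calls are not their only contact. The first window is three months wide, so a short stay need cost no assessment if the person re-enrolls. The window problem needs a missed 3-month assessment and release after month 5.5, and it falls on both arms alike. The plan already acknowledges the biases of a non-randomized comparison, mixed models can use partial follow-up, and Medicaid outcomes are planned for all enrolled participants for up to 2 years. Whether un-enrolled people stay in that set is not stated.

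What remains is a passive trigger, one-sided written notice, unequal routine contact and no plan for the resulting missing data.

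**Conclusion.** The concern holds as a risk, not as a demonstrated bias. Section 9.0 D together with the contact rules in section 9.0 H allows detection and return to differ by arm, and nothing in sections 6.0 or 7.0 handles the consequence. Under moderate assumed rates the spurious difference in comparison (B) is about 1 to 4 points in either direction, against a planned 14 (42% − 28%). It is zero if incarcerated participants answer like everyone else, and larger only under more extreme assumptions. Because the sign cannot be settled from the documents, it could not be corrected with confidence afterwards. That favors equal procedures now.

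The window finding rests on wording alone. Taken literally, sections 9.0 D and 5.4 conflict for a participant with no 3-month assessment who is released after month 5.5. Obtainable 6-month data are then discarded in both arms; this does not by itself create a difference between arms. Intervention participants enrolled in February-March 2023 have no 6-month survey, so it does not reach them.

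The 80% power figure is not in error.

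**What to change.** Keep the suspension during incarceration as written, and change five things around it.

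1. Give the same written notice of the rule, and the same contact on release, in both arms, using the locator form that both already complete.
2. Anchor the 6-month window to enrollment, so that a missed 3-month assessment does not forfeit the 6-month one, and reconcile section 9.0 D with section 5.4.
3. State that un-enrolled participants stay in their original group for analysis.
4. State that, where consent allows, they also stay in the linked-data analyses.
5. Report one sensitivity analysis that treats participants known to have been incarcerated alike in both arms. Identify them from study records plus the "WI Department of Corrections (DOC) administrative dataset" where available, and say that short county-jail stays may not be captured: section 5.4 gives state prison as its example and does not show jail coverage.

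The survey's criminal-justice items (Appendix 3 lists "probation in the last 6 months, days they were in jail") can supplement this but cannot define the group, because they are absent for the people who were lost.

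The cost is protocol wording, a few extra calls and one added analysis. The downside is that some late 6-month assessments will enter the data.

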## **E. Participant recruitment and consent**

**Provider interviews.** Directors or other key contacts at identified agencies providing services to opioid users will be contacted and asked to have one or more designated representatives from their agency participate in the qualitative interview. Providers will not be asked to provide any personal information, and therefore are not considered research subjects.

**Provider surveys.** Providers that will be invited to participate in the survey will be mailed a survey that will explain the study using a cover letter. The contact information of the study team will be provided for the participant to use, should they have any questions. The consent script will be provided at the beginning of the survey. If a provider agrees to take part in the project, they will simply fill out the survey and mail it back.

The provider survey will be administered by the UW Survey Center (UWSC). UWSC will administer, track, enter, and code the survey data. Questionnaires handled by data entry staff are tracked via case identification numbers only. Completed questionnaires are stored in locked file cabinets or locked storage rooms within their secure data entry facility for up to 7 years as required by Human Subjects protocols. After this period, hard copies of questionnaires will be destroyed. Sample files will be handled only by the UWSC project director and programmer for this study, and will not be merged with study data files for delivery to their clients. UWSC will send us a SAS database of our data using a secured file transmitting system. A last attempt to increase our response rate will include an email explaining the study and a website hyperlink to fill out a survey. The web-based survey will be housed on the same platform of the ACASI survey.

**Client interviews.** People who participate in the cross-sectional study described above will be systematically invited (e.g., every nth person) to also participate in a qualitative interview. Interested participants will be contacted by study staff to set up an interview appointment. Clients will be asked to sign an additional consent prior to enrollment in this study activity.

**Phase 1 (UG3) Participants.** Vivent Health prevention staff will meet with the person in a private room to explain more about the study. If they are interested, they will be given a consent document to read, and a phone call will be placed by Vivent Health staff to a study coordinator at UW-Madison. The participant and the researcher will then speak by phone in a private location to complete the eligibility screening and informed consent process. This will be done to minimize the impact of the research activities on the routine prevention activities of Vivent Health staff, and ensure that potential participants have enough time to have their questions answered prior to deciding whether or not to participate. During the initial phone call, potential participants will be provided with a detailed explanation of the study and questions will be answered. People who are willing to participate will be given formal informed consent using an iPad. Participants undergo a comprehension quiz on the iPad that assesses their understanding of the consent documentation. If a person agrees to take part in the project, he/she will be asked to sign the consent and HIPAA forms, which after the conclusion of the phone call with UW-Madison research staff, will be handed to the Vivent Health prevention team member to be filed in a locked file cabinet. Copies of the signed consent documents will be sent via secure fax to the study coordinator in Madison. A signed copy of the consent and HIPAA forms will be provided to the participant upon request. For participants ages 15 to 17, the consent form may be used to obtain consent of the minor, provided the study personnel determines that those minors can

comprehend the consent form. The consent form will be modified for participants ages 15-17 by adding a separate authorization section for the minor and the person obtaining assent.

For the retrospective analysis of stored HCV+ serum specimens obtained from WSLH and shared with GHOST laboratory collaborators, a waiver of consent and authorization is requested.

If participants are screened using a paper form at Vivent Health or at an outreach event, a paper copy of the consent document will be given to them and the Vivent Health staff will go over the study procedures. A study coordinator will be on standby to speak to the participant over the phone if they have any questions. If the participant agrees to be part of the study, the participant will be asked to sign the paper copy of the consent form. The form will be kept in the participant's folder in a double locked cabinet. Vivent Health already has a process in place since they work with HIV testing and case management. During outreach events, Vivent Health staff will securely transport screening documents and rapid test forms in a locked briefcase and store the forms in the participant's folders in a double locked cabinet. Once the participant has signed the paper copy of the consent form the iPad will begin at the ACASI survey, therefore the consent documentation will not be replicated.

*DHS Linkage Study on COVID-19 Pandemic Impact Among UG3 Participants.* For the analysis of the impact of the COVID-19 pandemic on the UG3 cohort, we will be providing DHS with identifiable data on UG3 participants, including participant name, date of birth, gender, race, ethnicity, previous address, previous phone number, date of participation in our study to facilitate linkage with approved registries (vital records, hospitalization, Wisconsin Electronic Disease Surveillance System, Wisconsin Immunization Registry). We are unable to re-obtain consent from participants for this data linkage because of the transient nature of this population and their lack of consistent access to a phone or other communication devices. It is not uncommon for the phone number that was used to initially recruit the participant to be inactive or out-of-date within days. It would be unfeasible to re-obtain consent participants from this cohort more than two years after initial recruitment. Considering this, we seek a Waiver of Consent and a partial waiver of authorization to link original cohort data with DHS data. We have also provided a justification as to how the original study's Certificate of Confidentiality is aligned with this linkage study. These justifications can be found within the Arrow application. Prior to sharing data or receiving data from DHS, we will obtain a signed Data Use Agreement that outlines the terms of the data sharing. A log of disclosures will be maintained in accordance with guidance from the HIPAA privacy officers consulted in the design of this study ([name], [name]; using the template: <https://compliance.wisc.edu/wp-content/uploads/sites/102/2019/02/Accounting-for-Disclosures-Log-Research.pdf>).

**Phase 2 (UH3) Participants.** Vivent Health staff will meet with participants in a private location within the SSP office for all aspects of the study. All forms will be delivered in person, and staff will gauge comprehension throughout the enrollment and verbal consent process. Participants will be given a copy of the verbal consent if they choose to participate. Paper copies of all documents will be stored in a locked cabinet, only accessible by the research team. Protections for the ACASI survey and blood specimens will be protected in the same manner as phase 1. The screening questionnaire will be the first document with both a name and study ID on them, and subsequent documents will only have one or the other, aside from testing documents. If necessary, all of the above activities may take place virtually, with electronic record keeping privacy considerations.

**COVID-19 Pilot.** All activities related to recruitment and consent will be conducted virtually either over the phone or via Microsoft Teams video call. Prevention navigators will hold responsibility for recruitment, unless UW staff assist by calling UG3 participants if necessary. UG3 participants who consented to future contact will be called using a random list by navigators. Additionally, participants will be passively recruited by study fliers distributed in prevention kits to clients, and by Vivent staff services. Those who are interested will be given a detailed description of what virtual navigation would look like, and will be screened for eligibility. If eligible, verbal consent will be taken only after the participant answers a series of questions about what the study involves to confirm comprehension. If ineligible, name and demographics will be retained on REDCap and a DOM secure drive to monitor duplicate screens and compare ineligible participants to those who enrolled. A paper copy of the consent form will be mailed to the participant upon authorization to do so or sent by text message/email if that is the client's preferred method of contact.

**ACHESS.** Upon account setup, participants will be able to choose a unique username that does not need to include their name or any other identifiable information. This username will be the name that appears in the pick list of participants available to private messaging, and listed on any discussion board posts. To protect participant's identity, it will be recommended that participants choose a username that will not include identifiable information such as first or last name, etc.

All subjects will have the option to contact study staff to turn off private messaging. This would prevent any incoming private messages, along with removing the participant's username from the picklist of participants who can be contacted by private message. Study staff will be able to monitor private messages, and participants can report any inappropriate or unwanted messages to study staff. The study team also has the option to turn off the private messaging function to those who send inappropriate or unwanted content to other participants to prevent future unwanted content.

